## Study Day

Post study day 1: study day = (date - date of Study Day 1) + 1

Pre study day 1: study day = (date – date of Study Day 1)

## Study Day 1

Page 17 of 35

Defined as the first day that protocol specified investigational products are administered to the subject. The day prior to Study Day 1 is considered Day -1.

#### Safety Follow-up (SFU)

The SFU visit should occur approximately 30 (+7) days after the last dose of AMG 562.

## Treatment-Emergent Adverse Event (TEAE)

A treatment-emergent adverse event is any adverse event **including disease related events** starting on or after the first dose of investigational product, as determined by the flag indicating if the adverse event started prior to the first dose on the Adverse Events Summary CRF, and up to and including 30 days after the end of investigational product.

## Treatment-Related AE

A treatment-related AE is any treatment-emergent AE that per investigator review has a reasonable possibility of being caused by the investigational product.

## Toxicity Probability Interval (TPI)

Toxicity probability intervals for dose-limiting toxicity (DLT) are defined as (0.20, 0.33], (0.33, 0.60] and (0.60, 1.00] for target, excessive and unacceptable toxicity, respectively.

#### Half-Life (t1/2)

The time required for the observed concentration of a drug to be reduced by one-half.

#### 6. Analysis Sets

The analysis of all endpoints, unless noted otherwise, will be conducted on the Safety Analysis Set.

## 6.1 All Enrolled Subjects

All enrolled subjects analysis set consists of the subjects who are enrolled into the study.

## 6.1.1 Primary Analysis Set

Not applicable to this study.

## 6.2 Safety Analysis Set

Safety analysis set is defined as all subjects that are enrolled and receive at least 1 dose of AMG 562.

## 6.3 Per Protocol Set(s)

Not applicable to this study.

## 6.4 DLT Analysis Set

CONFIDENTIAL

All subjects who are DLT-evaluable (see Section 6.2.1.3 of the protocol). DLT-evaluable subjects are those who 1) experienced DLTs or 2) completed DLT observational period and did not experience DLTs.

#### 6.5 Pharmacokinetic/Pharmacodynamic Analyses Set(s)

The PK Analysis Set will contain all subjects who have received at least 1 dose of AMG 562 and have at least 1 PK sample collected.

These subjects will be evaluated for PK analysis unless the number of data points required for analysis is not enough, or significant protocol deviations have affected the data, or if key dosing or sampling information is missing.

#### 6.6 Interim Analyses Set(s)

At interim analysis with cutoff determined, the DLT data will be analyzed based on DLT analysis set, and other data will be reported using safety analysis set, unless otherwise specified.

## 7. Planned Analyses

The following analyses are planned.

## 7.1 Interim Analysis and Early Stopping Guidelines

In the dose escalation part, safety data will be reviewed on an ongoing basis. Based on accumulating toxicity information, BLRM will be used to make dosing recommendations. In dose level review team meetings (DLRMs), Amgen, in consultation with the site investigators, will review the BLRM recommended dose level and will review all available cumulative data by cohort prior to making dose escalation decisions. As a sensitivity analysis, a one-parameter Continual Reassessment Method model may be used to estimate the dose-toxicity relationship to help making dose escalation decisions. Adverse events and DLTs observed in all subjects will be evaluated continually and fully integrated into all DLRMs and considered in all enrollment and dosing decisions.

The clinical activity of AMG 562 in the dose expansion part will be examined using a Bayesian predictive probability design. If the posterior probability is more than 85% that the ORR is 40% or less, then this is considered insufficient anti-lymphoma activity. If the ORR is too low, enrollment may be terminated early due to insufficient anti-lymphoma activity. The guidelines for futility due to insufficient efficacy assuming a prior beta distribution (0.8, 1.2) are presented in **Table 7-1**. The operating characteristics in **Table 7-2** provide the probability of stopping the trial early for given hypothetical true ORR rates.

The DLRT will be convened in the dose expansion part of the study to review efficacy data (with recruitment ongoing) after the first 15 subjects are enrolled and have had the opportunity to receive at least four weeks of treatment (with recruitment ongoing).

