# 10.4 Planned Analyses

### 10.4.1 Interim Analyses

In the dose escalation part, safety data will be reviewed on an ongoing basis. Based on accumulating toxicity information, BLRM will be used to make dosing recommendations. In dose level review team meetings (DLRMs), Amgen, in consultation with the site investigators, will review the BLRM recommended dose level and will review all available cumulative data by cohort prior to making dose escalation decisions. As a sensitivity analysis, a one-parameter Continual Reassessment Method model may be used to estimate the dose-toxicity relationship to help making dose escalation decisions. Adverse events and DLTs observed in all subjects will be evaluated continually and fully integrated into all DLRMs and considered in all enrollment and dosing decisions.

The clinical activity of AMG 562 in the dose expansion part will be examined using a Bayesian predictive probability design. If the posterior probability is more than 85% that the ORR is 40% or less, then this is considered insufficient anti-lymphoma activity. If the ORR is too low, enrollment may be terminated early due to insufficient anti-lymphoma activity. The guidelines for futility due to insufficient efficacy assuming a prior beta distribution (0.8, 1.2) are presented in Table 15. The operating characteristics in Table 16 provide the probability of stopping the trial early for given hypothetical true ORR rates whereas the stopping criteria in Table 15 are based on situations where the empirical evidence would result in a posterior probability of  $\geq$ 85% that the true ORR rate is  $\leq$  40%.

The DLRT will be convened in the dose expansion part of the study to review efficacy data (with recruitment ongoing) after the first 15 subjects are enrolled and have had the opportunity to receive at least five weeks of treatment (with recruitment ongoing).

Number of Treated Subjects	Efficacy Futility Guideline					
15	4 or fewer responders					
20	5 or fewer responders					
25	7 or fewer responders					
30	9 or fewer responders					
35	11 or fewer responders					
40	12 or fewer responders					
45	14 or fewer responders					
50	16 or fewer responders					
55	Trial will stop					

 Table 15. Guideline for Insufficient Efficacy

Table 16.	Operating	Characteristics for futi	ility With Batch Size of 5 Subject	S
	oporading			

True ORR Rate	Probability of Stopping Early for Futility	Average Sample Size
0.25	95%	21
0.30	81%	27
0.35	59%	36
0.40	36%	43
0.45	18%	49

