## 3. Study Overview

## 3.1 Study Design

This is a multicenter, Phase 1, first-in-human (FIH), non-randomized, open-label study in adult subjects with relapsed / refractory DLBCL, MCL, or FL. AMG 562 will be administered weekly as short term IV infusions (1.5 hour).

The study will consist of up to a 21-day screening period, a treatment period, a safety follow-up (SFU) visit conducted 30 (+7) days after the last dose of AMG 562, and a long-term follow-up (LTFU) period that will begin after the SFU visit is completed. Subjects will be followed for response evaluation at week 5, week 15, week 25 and at end of treatment if end of treatment is at week 35 or beyond (± 3 days). Subjects who

stopped response evaluations will be followed every 3 months (± 2 weeks) for survival follow-up. The total duration of the LTFU will be up to 2 years from the first dose of AMG 562.

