## **Objective Response Rate**

ORR is defined as the incidence rate of a confirmed CMR or PMR while on study as defined by Lugano Classification.

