#### Table 7-1. Guideline for Insufficient Efficacy

Number of Treated Subjects	Efficacy Futility Guideline	
15	4 or fewer responders	
20	5 or fewer responders	
25	7 or fewer responders	
30	9 or fewer responders	
35	11 or fewer responders	
40	12 or fewer responders	
45	14 or fewer responders	
50	16 or fewer responders	
55	Trial will stop	

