## 8.3 Handling of Missing and Incomplete Data

Incomplete adverse event and concomitant medication dates missing data will be imputed as described in Appendix A. For efficacy data of overall response, subjects without tumor response assessments will be considered as non-responders. Otherwise, only nonmissing data will be analyzed.

Ineligible subjects and subjects enrolled in Part 1 who are not DLT evaluable may be replaced.

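### The first futility look can be held before all 15 subjects have been scanned, while its boundary and stopping probabilities assume every response is already known

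*SAP*

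**What the plan says.** **Trigger.** SAP 7.1 convenes the efficacy review when the first 15 expansion subjects "have had the opportunity to receive at least four weeks of treatment (with recruitment ongoing"). Protocol 10.4.1 requires that they "have had the opportunity to receive at least five weeks of treatment", and the protocol synopsis and section 3.1 also give five weeks. SAP 3.1 (Part 2) gives five weeks too, but attaches it to the safety review. SAP section 10, which lists departures from the protocol, does not mention the change.

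**Scans.** "Subjects will be followed for response evaluation at week 5, week 15, week 25", with a window of ± 3 days. Protocol 7.3.12.3 equates week 5 with cycle 2 day 1.

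**Missing scans.** Under SAP 8.3, "subjects without tumor response assessments will be considered as non-responders".

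**Rule.** "If the posterior probability is more than 85% that the ORR is 40% or less, then this is considered insufficient anti-lymphoma activity", "assuming a prior beta distribution (0.8, 1.2"). Table 7-1 turns this into "4 or fewer responders" at 15 subjects. Table 7-2 gives an 8% chance of early stopping at a true ORR of 50%. Protocol Tables 15 and 16 carry the same figures.

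**Response definition.** SAP section 5: "ORR is defined as the incidence rate of a confirmed CMR or PMR while on study as defined by Lugano Classification". No confirmation rule or interval is given. The SAP's definition of objective response, its ORR analysis in 9.5.2 and protocol 10.5.3.2 all use CMR or PMR without confirmation. Neither document says which definition the futility count uses.

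**The concern.** A futility count is only as good as the responses already visible when it is taken. Under the SAP trigger, four weeks end at about day 28 and the first scan is nominally on day 29. A subject who has just met the minimum may be unscanned and is then scored as a non-responder. Under the protocol trigger each subject has reached one scan, and the next comes ten weeks later. ORR counts response at any time on study, so a first response at week 15 or 25 belongs in the final ORR but cannot be seen at week 5.

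Both gaps push the count down. The boundary has little slack: with 4 responders of 15 the stopping criterion is only just met, and with 5 it is clearly not. One responder not yet visible can reverse the recommendation. The dose level review team would be reading the count against stopping probabilities that do not describe it, and the error runs towards halting enrolment on an active drug.

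**Working it through.** **Inputs.** Beta(0.8, 1.2) prior, 85% threshold and 40% reference ORR (SAP 7.1); boundaries 15/4, 20/5, 25/7, 30/9, 35/11, 40/12, 45/14 and 50/16, with a maximum of 55 (Table 7-1); looks every 5 subjects (Table 7-2).

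**1. Reproduce the plan's figures.** With r responders of n the posterior is Beta(0.8 + r, 1.2 + n − r).
- n = 15, r = 4: Pr(ORR ≤ 0.40) = 0.859, above 0.85, so stop.
- n = 15, r = 5: 0.708, so continue.
- All eight boundaries match Table 7-1.

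An exact sequential binomial calculation, with every response known at each look, gives overall stopping probabilities of 94.9, 81.5, 59.2, 35.7, 18.0, 7.9 and 3.1% at true ORR 0.25 to 0.55. Table 7-2 states 95, 81, 59, 36, 18, 8 and 3%. The table is right for complete ascertainment. The 7.9% at ORR 0.50 is cumulative over all looks; the first look alone contributes P(Bin(15, 0.50) ≤ 4) = 5.9%, and this is the comparator for the first-look figures below.

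**2. Unscanned subjects (four-week trigger).** With 28-day cycles the scan window is days 26 to 32, so a scan may fall before or after four weeks. Let k of the 15 be unscanned and scored as non-responders, and let every eventual responder among the scanned already show. The first-look stopping chance at ORR 0.50 is P(Bin(15 − k, 0.50) ≤ 4):

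| Unscanned k | Chance of stopping |
|---|---|
| 0 | 5.9% |
| 1 | 9.0% |
| 2 | 13.3% |
| 3 | 19.4% |

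**3. One scan each (five-week trigger).** Let f be the share of eventual responders already in response at week 5. The documents do not give f, so a range is assumed. If all 15 have only the week-5 scan, the first-look chance is P(Bin(15, 0.50 f) ≤ 4):

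| f | First look | All looks, only the first affected |
|---|---|---|
| 1.0 | 5.9% | 7.9% |
| 0.9 | 12.0% | 13.5% |
| 0.8 | 21.7% | 22.7% |
| 0.7 | 35.2% | 35.8% |

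The last column lets the late responders among the first 15 appear by the second look. Each subject not in response at week 5 converts with probability (0.50 − 0.50 f)/(1 − 0.50 f), which at f = 0.8 is 0.10/0.60 = 1/6. Later looks are taken as fully known.

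**4. If confirmation meant a second scheduled scan.** Only subjects past week 15 could then count. If m of the 15 have reached it and f = 1, the stopping chance at ORR 0.50 is P(Bin(m, 0.50) ≤ 4), which is 100% whenever m is below 5. With even accrual and a four-week minimum, a subject enrolled d weeks before the fifteenth has reached week 15 if 4 + d ≥ 15:

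| Accrual | m | Chance of stopping |
|---|---|---|
| 1 per week | 4 | 100% |
| 1 per 2 weeks | 9 | 50% |
| 1 per 4 weeks | 12 | 19% |

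**The case against.** **Four or five weeks is a minimum.** The first 15 enrol over time, and earlier subjects may have week-15 scans. This stands. The table in step 3 is the extreme in which nobody has a second scan, and it would be wrong to say that the look counts only week-5 responders.

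**The share f is assumed.** This also stands. If nearly all responders respond by week 5, the five-week trigger does little harm. The unscanned-subject figures in step 2 do not depend on late response, only on how many scans are missing.

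**A reader might infer that stopping is certain under the SAP's ORR definition.** The documents do not support that. They give no confirmation rule, do not tie the look to confirmed response, and omit the word in the SAP's objective response definition, SAP 9.5.2 and protocol 10.5.3.2. Certainty would need three things together: confirmation by a second scheduled scan, fewer than 5 of 15 past week 15, and a guideline treated as binding.

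**The rule is not binding.** SAP 7.1 says enrolment may be terminated, and the review team sees all available data, including stable subjects awaiting their next scan. That softens the consequence but does not make Table 7-2 describe the look as planned.

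**The study stopped early.** SAP sections 1 and 7.2 record this. It lowers the practical stakes, not the validity of the point.

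**Conclusion.** The concern holds in a limited form. The four- and five-week triggers conflict, and the SAP's version can place the look before the newest subjects' first scan. Tables 7-1 and 7-2 are correctly computed, but for complete ascertainment, so the 8% at ORR 50% is a floor rather than the expected chance. The excess depends on the number of missing scans, the accrual rate and f, none of which the documents give. A claim that the false-stop rate is well above 8% as a matter of fact would go too far, as would setting first-look figures directly against that cumulative 8%. Like for like at f = 0.8, with all 15 having only the week-5 scan and only the first look affected, the chance is 21.7% against 5.9% at the first look, and 22.7% against 7.9% overall. The undefined confirmation requirement is a separate ambiguity that needs resolving. Severity is moderate, given the non-binding guideline and the early discontinuation.

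**What to change.** 1. In SAP 7.1, replace the four-week exposure minimum with a completed week-5 response assessment, or earlier progression, death or discontinuation, for each of the 15 subjects. Reconcile this with the protocol's five weeks.
2. State that the futility count uses CMR or PMR by Lugano without a confirmation requirement, as in protocol 10.5.3.2. In SAP section 5, either remove *confirmed* from the ORR definition or give the rule.
3. Label Table 7-2 as assuming fully ascertained response, and add stopping probabilities for a range of week-5 ascertainment shares, such as those in step 3.
4. Keep stable subjects in the denominator. Setting aside all non-progressing subjects as pending would leave mainly responders and early failures, and would inflate the ORR at the look.

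The cost is small: SAP wording and a short recalculation, a first look that may come slightly later, and stated stopping probabilities that look less favourable. Changing the boundaries themselves would also touch protocol Tables 2 and 15 and so need an amendment; these steps do not require that.

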#### Table 7-1. Guideline for Insufficient Efficacy

Number of Treated Subjects	Efficacy Futility Guideline	
15	4 or fewer responders	
20	5 or fewer responders	
25	7 or fewer responders	
30	9 or fewer responders	
35	11 or fewer responders	
40	12 or fewer responders	
45	14 or fewer responders	
50	16 or fewer responders	
55	Trial will stop	

#### Table 7-2. Operating Characteristics With Batch Size of 5 Subjects

True ORR Rate	Probability of Stopping Early for Futility	Average Sample Size
0.25	95%	21
0.30	81%	27
0.35	59%	36
0.40	36%	43
0.45	18%	49
0.50	8%	52
0.55	3%	54

Additionally, the DLRT will review safety data and conduct evaluations of the ongoing DLT rate to assess if the threshold for early trial termination has been reached. The stopping rules use a Bayesian approach to terminate the study if the posterior probability that the DLT rate is greater than 33% is > 90%. The stopping boundaries assuming a prior beta distribution (0.66, 1.33) are presented in **Table 7-3**. The operating characteristics in **Table 7-4** provide the probability of stopping the trial early for given hypothetical true DLT rates. The evaluations could occur more frequently if necessary to address emerging safety concerns.

## Table 7-3. Stopping Boundaries

Number of DLT Evaluable Subjects	Stop Study If Observing These Many DLTs
10	≥ 6
15	≥ 8
20	≥ 10
25	≥ 12
30	≥ 14
35	≥ 16
40	≥18
45	≥ 20
50	≥ 21
55	Trial will stop

#### Table 7-4. Operating Characteristics With Batch Size of 5 Subjects

True DLT Rate	Probability of Stopping Early	Average Sample Size			
0.20	1%	55			
0.25	4%	53			
0.3	13%	51			
0.33	22%	48			
0.35	31%	45			
0.40	56%	37			
0.45	79%	29			

## 7.2 Primary Analysis

Originally the primary analysis would occur when target enrollment is complete and each subject either completes 3 months on study or withdraws from the study. Due to the discontinuation of the study, the primary analysis will occur at the time of study termination decision and include all required available data up to the point of that snapshot which is going to be taken for the primary analysis. This snapshot will have all data up to the LFTU for all subjects except one ongoing subject.

## 7.3 Final Analysis

Originally, the final analysis would occur after all subjects have ended the study. Due to the discontinuation of the study, the final analysis will occur when the last enrolled patient has ended the study.

## 8. Data Screening and Acceptance

## 8.1 General Principles

The objective of the data screening is to assess the quantity, quality, and statistical characteristics of the data relative to the requirements of the planned analyses.

## 8.2 Data Handling and Electronic Transfer of Data

The Amgen Global Study Operations-Data Management (GSO-DM) department will provide all data to be used in the planned analyses. This study will use the RAVE database. The database will be subject to edit checks outlined in the Clinical Data Management Plan (DMP). See details of this section in the DMP.

## 8.3 Handling of Missing and Incomplete Data

Incomplete adverse event and concomitant medication dates missing data will be imputed as described in Appendix A. For efficacy data of overall response, subjects without tumor response assessments will be considered as non-responders. Otherwise, only nonmissing data will be analyzed.

Ineligible subjects and subjects enrolled in Part 1 who are not DLT evaluable may be replaced.

#### 8.4 Detection of Bias

Lack of protocol compliance and the potential for biased statistical analyses will be examined by assessing the incidence of important protocol deviations. The clinical study team will identify and document the criteria for important protocol deviations.

#### 8.5 Outliers

Pharmacokinetic (PK) serum concentration data will be evaluated for outliers by visual inspection, and decisions to re-assay individual samples will be made in accordance with standard pharmacokinetic evaluation practice. Suspected outliers will be included in all analyses unless there is sufficient scientific justification to exclude them.

#### 8.6 Distributional Characteristics

Where appropriate, the assumptions underlying the proposed statistical methodologies will be assessed. If required data transformations or alternative non-parametric methods of analyses will be utilized.

#### 8.7 Validation of Statistical Analyses

Programs will be developed and maintained and output will be verified in accordance with current risk-based quality control procedures.

Tables, figures, and listings will be produced with validated standard macro programs where standard macros can produce the specified outputs.

The production environment for statistical analyses consists of Amgen-supported versions of statistical analysis software; for example, the SAS System version 9.3 or later.

## 9. Statistical Methods of Analysis

## 9.1 General Considerations

Descriptive statistics will be provided for selected demographics, safety, and PK data by dose, dose schedule, and time as appropriate. Unless otherwise stated, the data analysis will be conducted using subjects in the Safety analysis set by cohorts and overall. Descriptive statistics on continuous data will include means, medians, standard deviations and ranges, while categorical data will be summarized using frequency counts and percentages. Graphical summaries of the data may also be presented.

## 9.2 Subject Accountability

The number and percent of subjects who were enrolled, received investigational product, completed investigational product, discontinued from investigational product (including reasons for discontinuing), completed study, discontinued the study (including reasons for discontinuing), **completed safety follow-up and long term follow-up** will be summarized by cohort and **dose**.

Key study dates for the first subject enrolled, last subject enrolled and last subject's end of study will be summarized.

A summary noting inclusion in each analysis subset will be provided for all subjects enrolled.

## 9.3 Important Protocol Deviations

Important Protocol Deviations (IPDs) categories are defined by the study team before the first subject's initial visit and updated during the IPD reviews throughout the study prior to database lock. These definitions of IPD categories, subcategory codes, and descriptions will be used during the course of the study. Eligibility deviations are defined in the protocol. The final IPD list is used to produce the Summary of IPDs table and the List of Subjects with IPDs. In addition, a separate listing of all inclusion and exclusion deviations will be provided.

